## **6. Statistical analysis**

### **r. General**

The general approach is to quantify the cumulative incidence of the composite primary endpoint using Cox proportional hazards models stratified by study centers and randomization factor as previously described.

Statistical analyses will be performed using SPSS / PC version 22.0 or higher and/or R version 3.4 or higher.

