### **8.2 Statistical Analysis**

The statistical analyses will be performed using the SPSS / PC (version 14.0, SPSS Inc., USA) software package. A statistical significance level (p-value) of 0.05 will be used. All data will be analyzed on an intention-to-treat basis. Comparisons will be made using the t-test, Mann Whitney U-test, Fisher's exact test, survival analysis (Kaplan Meier method), Cox regression analysis and chi-square test as appropriate. All hypothesis testing will be two-tailed. Statistical support will be performed by [name] from the Institute of Social and Preventive Medicine of the University of Basel.

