### **f. Sample size**

Sample size calculation is based on the on the data from the BASEL V study. A hypothesized 20%-decrease of the composite endpoint death or HF re-hospitalization at 180 days, will require 385 patients per treatment arm to obtain, with a probability of 80%, a log rank test result that is statistically significant at the 5%-level. In order to compensate for an expected 1-2% of patients in whom the primary endpoint could not be assessed at 180 days due to loss to follow-up or complete withdrawal of ICF, it was planned to enroll approximately 780 patients.

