**ii. Adjustments for covariates**

The primary analysis will be adjusted for four strong predictors of the composite primary endpoint (death or HF-rehospitalisation within 6 months): age, HF hospitalization in the year before inclusion, systolic blood pressure, and serum creatinine.

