**iii. Multicenter studies**

HR by center will be visually plotted to assess how strong the heteroscedasticity is. No adjustment of center effects are reported, except in the Sensitivity analyses

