22 Six days after admission or until discharge from the index hospitalization.

23 **iii. Dose of exposure and concentration**

- 24 – sublingual nitrates: 0.8 mg glyceryl trinitrate, sublingual, 3 times every ten minutes.
- 25 Sublingual nitrates have an approximate onset of action of 1-3 minutes and a half-life
- 26 of 1–4 min.
- 27 – hydralazine 25 mg p.o. four times a day (QID) for 2 days. Half-life, 2–8 hours,
- 28 – nitroglycerin patches in a dosage between 40 to 80 mg in 24 h depending on systolic
- 29 blood pressure and for 5 days. Elimination half-life takes around 10 minutes.
- 30

31

32

33 **9. Evaluation of patients at follow-up**

34 Patient are contacted at 90, 180 and 360 days follow-up (telephone calls, letters). During the  
35 FU patients will be asked about current medication, functional NYHA class and additionally,  
36 to complete Quality of life (EQ-5D-3L) and Kansas City Cardiomyopathy Questionnaire  
37 (KCCQ).

38 **aa. Follow-up at 90 days**

39 The follow-up 90 days months contains a self-reported medicament list update, potential  
40 endpoints assessment, a functional NYHA class assessment and Quality of Life (EQ-5D-3L)  
41 assessment.

42 **bb. Follow-up at 180 days**

43 The follow-up 180 days months contains a self-reported medicament list update, potential  
44 endpoints assessment, a functional NYHA class assessment and Quality of Life (EQ-5D-3L)  
45 and KCCQ assessment.

46 **cc. Follow-up at 360 days**

47 The follow-up 360 days months contains a self-reported medicament list update, a functional  
48 NYHA class assessment and Quality of Life (EQ-5D-3L) and KCCQ assessment.

49 .

50

51 **10. Evaluation of efficacy parameters**

52 **dd. Analysis of primary, secondary, and other efficacy endpoints**

53 **i. Analysis of primary endpoint**

54 The primary endpoint will be analyzed using survival analysis for cumulative incidence (e.g.  
55 Cox regression, Kaplan-Meier and Hazard Ratio) and log rank testing for significance at 180  
56 days.

57 **ii. Analysis of secondary endpoints**

58 Secondary endpoints will be analyzed using the same approach as for the Primary endpoints  
59 and interaction test (p-value) will be conducted between the treatment group and the sub-  
60 group variables.

61 **iii. Analysis of other endpoints**

62 All other endpoints, including novel biomarkers or neurohormones not yet specified in the  
63 protocol will be analyzed using the same approach as for the **Secondary endpoints**.

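### The SAP contradicts itself on centre, covariates and follow-up window in the primary analysis, so the deciding p-value is not fixed

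*Combined protocol and SAP*

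**What the plan says.** Five places in the SAP bear on the primary test.

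- **SAP 6.1 (General):** the composite primary endpoint is analysed with "Cox proportional hazards models stratified by study centers and randomization factor as previously described".
- **SAP 6.6.2 (Adjustments for covariates):** "The primary analysis will be adjusted for four strong predictors of the composite primary endpoint". The four are age, heart failure hospitalisation in the preceding year, systolic blood pressure and creatinine.
- **SAP 6.6.3 (Multicenter studies):** "No adjustment of center effects are reported, except in the Sensitivity analyses".
- **SAP 10.1.1 (Analysis of primary endpoint):** survival methods are given as examples, "Cox regression, Kaplan-Meier and Hazard Ratio) and log rank testing for significance at 180" days. Whether the log-rank test is stratified is not stated.
- **SAP 10.2.4 (Time-to-event data):** the arms are compared by a Cox model with length of follow-up as an offset, counted to the one-year contact or the last contact. No strata or covariates are named.

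Table 3 has one hazard ratio and one p-value for the primary endpoint and names no model. Protocol 8.2 lists several tests to be used as appropriate and assigns none to the primary endpoint. It does fix the level: "A statistical significance level (p-value) of 0.05 will be used", and "All hypothesis testing will be two-tailed". The sample size in SAP 3.2 rests on a log-rank test.

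**The concern.** SAP 6.6.4 makes every secondary p-value exploratory, with no significance threshold, so the confirmatory claim rests on the primary p-value alone. If the text permits more than one way to compute it, two analysts following the SAP can reach different conclusions from the same data, and a version can be chosen once results are known. The trial is open label. Blinded adjudication (SAP 3.4) protects the classification of events but not the choice of model.

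The estimate is ambiguous too. A hazard ratio conditional on strong covariates and an unadjusted one are different quantities, and Table 3 has room for one.

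**Working it through.** **1. The passages side by side**

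| Item | One place | Another place | Compatible? |
|---|---|---|---|
| Centre | 6.1: model stratified by centre | 6.6.3: centre adjusted only in sensitivity analyses | No, on the ordinary reading |
| Covariates and source of p-value | 6.6.2: primary analysis adjusted for four covariates | 10.1.1: significance from log-rank | No; a log-rank test carries no covariates |
| Time window | Endpoint, and test in 10.1.1: 180 days | 10.2.4: offset, to one year or last contact | No, unless 10.2.4 excludes the primary endpoint, which it does not say |
| 6.1 with 6.6.2 | Strata | Covariates | Yes; one Cox model can have both |

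**2. The sizing figure**

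SAP 3.2 states: "A hypothesized 20%-decrease of the composite endpoint death or HF re-hospitalization at 180 days, will require 385 patients per treatment arm". The target is 80% power for a log-rank test at the 5% level. The control event rate is not given, so 385 cannot be derived from the documents alone. Reading 20% as a relative risk reduction under proportional hazards, with control rate p:

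- HR = ln(1 − 0.8p) / ln(1 − p); events needed D = 4(1.960 + 0.842)² / (ln HR)² = 31.4 / (ln HR)².
- At p = 0.50: HR = ln 0.60 / ln 0.50 = 0.737, ln HR = −0.3052, D = 31.4 / 0.0931 = 337. Total N = 337 / 0.45 = 749, or about 375 per arm.
- Solving for exactly 385 per arm gives p = 49.3% (Schoenfeld) or 49.7% (Freedman).
- At 385 per arm and 50% v 40%, events = 192.5 + 154 = 346.5. Power = Φ(½√346.5 × 0.3052 − 1.960) = Φ(0.88) = 81.1%.

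A control rate of about 50% is therefore the back-solved assumption used below. At 770 patients, power would be 47% at a control rate of 30%, 65% at 40% and 88% at 55%.

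**3. What the open choice is worth**

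*Inputs from the documents:* 770 patients, 1:1 allocation, randomisation stratified by site and BNP level, 17 sites listed in protocol section 3, two-sided 5%.

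*Assumptions:* 50% v 40% events at 180 days, unequal site sizes, equal halves by BNP level, blocks of four, exponential event times, and three levels of prognostic strength. Strength is set by the SD of the covariate log-hazard, the SD of site effects and the BNP log hazard ratio: none (0, 0, 0), moderate (0.4, 0.2, 0.3) and strong (0.7, 0.3, 0.5).

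There were 12,000 trials per scenario under the null and 6,000 under the alternative. The four analyses were a log-rank test taken as unstratified (A), stratified Cox (B), Cox with four covariates (C), and Cox with strata and covariates (D). The offset model of 10.2.4 was not simulated.

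| Prognostic strength | Power A / B / C / D | Type I error, smallest of four p-values | Trials with disagreement under the alternative |
|---|---|---|---|
| None | 80.1 / 79.5 / 80.1 / 79.9% | 5.9% | 5% |
| Moderate | 81.7 / 81.2 / 84.9 / 84.3% | 6.9% | 9% |
| Strong | 83.5 / 83.7 / 90.8 / 91.2% | 8.7% | 14% |

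Any single analysis fixed in advance had type I error of 4.4-5.2%. Stratification alone (B − A) moves power by about half a point or less. Adding strata and covariates (D − A) moves it by −0.2, +2.6 and +7.7 points. In a shorter run of 2,000 trials in the strong scenario, the average hazard ratio was 0.728 from B and 0.695 from D.

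**The case against.** Much of the SAP can be read consistently. Sections 6.1 and 6.6.2 combine into one stratified, adjusted Cox model, and the site-pooling rule in 6.2 fits it. A log-rank p-value beside a Cox hazard ratio is a common pairing and a possible reading of 10.1.1. Section 6.6.3 might concern only the reporting of centre effects, or might not count stratification as adjustment. Section 10.2.4 covers time-to-event data in general, including a 360-day endpoint.

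These points narrow the problem without removing it. Even if 6.6.3 is read generously, 6.6.2 calls the adjusted analysis primary while 10.1.1 takes significance from a test that cannot be adjusted. Section 10.2.4 makes no exception for the primary endpoint.

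A reader might infer three stronger things that the documents do not support:

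- **That the SAP specifies an unstratified log-rank test.** It does not say, and a stratified log-rank test exists.
- **That all the descriptions exclude one another.** Sections 6.1 and 6.6.2 do not.
- **That a log-rank test leaves the trial underpowered.** The trial was sized on that test, and at event rates that reproduce the stated sample size its power is 80-84% in the simulation. Any gain from covariates depends on prognostic strengths that the documents do not give.

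The 6-9% figure supposes deliberate selection of the smallest p-value. Nothing in the documents suggests that this is intended.

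**Conclusion.** The point holds as a contradiction in the text. Sections 6.1 and 6.6.3 conflict on centre, 6.6.2 and 10.1.1 on covariates and the source of significance, and 10.2.4 conflicts with the 180-day endpoint. The single confirmatory p-value is not fixed.

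That conclusion rests on the wording alone and is firm. The size is less certain. Error of about 6-9% instead of 5% is a worst case over four versions, and disagreement in about 5-14% of trials assumes 50% v 40% events. Both depend on assumed prognostic strength. Some inflation (5.9%) appears even with no prognostic effect. Power is a secondary matter: 0 to about 8 points gained from covariates, and almost nothing from stratification.

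**What to change.** In SAP 6.1 and 10.1.1, name one confirmatory analysis that combines what 6.1 and 6.6.2 already require:

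- a Cox model for time from randomisation to first event, censored at day 180 or last contact if earlier;
- stratified by site (pooled as in 6.2) and by the BNP/NT-proBNP randomisation stratum;
- adjusted for age, heart failure hospitalisation in the preceding year, systolic blood pressure and creatinine;
- with its two-sided p-value for arm, at 5%, as the test.

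Then:

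- label the log-rank test (saying whether it is stratified) and the unadjusted hazard ratio as supportive;
- delete the second sentence of 6.6.3;
- for the primary endpoint, replace the offset and one-year window in 10.2.4 with the censoring rule above;
- name the model in Table 3.

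The cost is SAP wording, provided it is settled before unblinding. There are two small downsides. The confirmatory test then differs from the log-rank test used for sizing, which is acceptable if the SAP says so. Patients with a missing covariate must also stay in the intention-to-treat analysis, for example by applying the chained-equations imputation already planned to the covariates. Heart failure hospitalisation in the preceding year is not in baseline Table 1, so confirm that it is recorded; 6.6.2 already needs it.

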### **s. Pooling of sites**

Any sites with fewer than 10 subjects will be pooled by country/region. If a country/region has fewer than 10 subjects, that country/region will be pooled with its nearest neighboring country/region.

### **t. Interim analyses**

No interim analyses are planned.

### **u. Time-points for analysis**

Time-points for primary and secondary endpoint assessments are the follow-up at 180 and 360 days.

### **v. Methods for handling missing data and sensitivity analyses**

Sensitivity analyses will be conducted in: patients without evidence of systemic, infection/inflammation at presentation (defined as CRP  $< 20$  mg/L), in patients without major protocol deviation and in patients enrolled in outside Europe and Central Europe.

To deal with data with  $> 10\%$  missing values, sensitivity analyses will be conducted using multiple imputations by chained equations methods and 20 data-sets will be created.

### **w. Statistical analytical issues**

#### **i. Assessment of statistical assumptions**

Violation of the proportional hazards assumption in Cox models will be assessed by examining clog-log transformed Kaplan-Meier figures and by examination of Schoenfeld residuals.

**ii. Adjustments for covariates**

The primary analysis will be adjusted for four strong predictors of the composite primary endpoint (death or HF-rehospitalisation within 6 months): age, HF hospitalization in the year before inclusion, systolic blood pressure, and serum creatinine.

**iii. Multicenter studies**

HR by center will be visually plotted to assess how strong the heteroscedasticity is. No adjustment of center effects are reported, except in the Sensitivity analyses

**iv. Multiple comparisons**

All secondary analyses are explorative and therefore no multiple comparisons will be performed. P-values of secondary analyses will be interpreted as a continuous measurement of the level of surprise for seeing the observed result, and not in relation to a threshold of significance.

**v. Use of efficacy subset**

All patients will be analyzed by intention-to-treat and reported according to their randomized arm, irrespective of whether and how much of the study drug they received. Note that the last assessment of the endpoints will be used if otherwise no measurement of the endpoint could be conducted at 180 days, due to withdrawal of consent or due to lost to follow-up incl. failure to collect all the required documents for endpoint adjudication.

**vi. Active-control studies intended to show equivalence**

Not applicable.

**vii. Examination of subgroups**

Time to primary endpoint of intervention arm vs standard of care arm will be explored for all the patients and again for the predefined subgroups plus interaction test HR within groups.

---

 Voors, AA, Ouwerkerk, *et al.* Development and validation of multivariable models to predict mortality and hospitalization in patients with heart failure. *Eur J Heart Fail* 2017; 19: 627– 634.

## 7. Evaluation of characteristics and medication

### x. Baseline clinical characteristics

P-values, standard errors, and confidence intervals are not shown in baseline tables following the CONSORT Statement.

The following baseline table will be produced:

**Table 1. Baseline Clinical Characteristics and Medical History**

	Total Patients (N=)	Intervention arm (N=)	Standard of care arm (N=)
Age – years ( $\pm$ SD)	XX $\pm$ XX	XX $\pm$ XX	XX $\pm$ XX
Male gender – no. (%)	xx (xx%)	xx (xx%)	xx (xx%)
BMI - kg ( $\pm$ SD)	XX $\pm$ XX	XX $\pm$ XX	XX $\pm$ XX
Cardiovascular Risk Factors:			
Diabetes mellitus – no. (%)	xx (xx%)	xx (xx%)	xx (xx%)
Dyslipidemia – no. (%)	xx (xx%)	xx (xx%)	xx (xx%)
Ever smoked – no. (%)	xx (xx%)	xx (xx%)	xx (xx%)
Hypertension – no. (%)	xx (xx%)	xx (xx%)	xx (xx%)
Structural heart disease:			
Hypertensive heart disease – no. (%)	xx (xx%)	xx (xx%)	xx (xx%)
Chronic Heart failure – no. (%)	xx (xx%)	xx (xx%)	xx (xx%)
CAD – no. (%)	xx (xx%)	xx (xx%)	xx (xx%)
PCI – no. (%)	xx (xx%)	xx (xx%)	xx (xx%)
Coronary Bypass – no. (%)	xx (xx%)	xx (xx%)	xx (xx%)
Myocardial infarction – no. (%)	xx (xx%)	xx (xx%)	xx (xx%)
Valvular replacement – no. (%)	xx (xx%)	xx (xx%)	xx (xx%)
Atrial Fibrillation – no. (%)	xx (xx%)	xx (xx%)	xx (xx%)
ICD/CRT – no. (%)	xx (xx%)	xx (xx%)	xx (xx%)
Chronic Comorbidities:			
COPD/ Asthma – no. (%)	xx (xx%)	xx (xx%)	xx (xx%)
Renal insufficiency – no. (%)	xx (xx%)	xx (xx%)	xx (xx%)
Peripheral vascular disease – no. (%)	xx (xx%)	xx (xx%)	xx (xx%)
Stroke – no. (%)	xx (xx%)	xx (xx%)	xx (xx%)
Pneumonia – no. (%)	xx (xx%)	xx (xx%)	xx (xx%)
Pulmonary embolism – no. (%)	xx (xx%)	xx (xx%)	xx (xx%)
Liver disease – no. (%)	xx (xx%)	xx (xx%)	xx (xx%)
Active malignancy – no. (%)	xx (xx%)	xx (xx%)	xx (xx%)
Symptoms at admission or shortly before			
NYHA class – no. (%)			
III	xx (xx%)	xx (xx%)	xx (xx%)
IV	xx (xx%)	xx (xx%)	xx (xx%)
Days with dyspnea – days ( $\pm$ SD)	XX $\pm$ XX	XX $\pm$ XX	XX $\pm$ XX
Chest pain – no. (%)	xx (xx%)	xx (xx%)	xx (xx%)
Nycturia – no. (%)	xx (xx%)	xx (xx%)	xx (xx%)
Weight gain – no. (%)	xx (xx%)	xx (xx%)	xx (xx%)

Orthopnea – no. (%)	xx (xx%)	xx (xx%)	xx (xx%)
Paroxysmal nocturnal dyspnea – no. (%)	xx (xx%)	xx (xx%)	xx (xx%)
Coughing – no. (%)	xx (xx%)	xx (xx%)	xx (xx%)
Sputum – no. (%)	xx (xx%)	xx (xx%)	xx (xx%)
Fever – no. (%)	xx (xx%)	xx (xx%)	xx (xx%)
Night sweats – no. (%)	xx (xx%)	xx (xx%)	xx (xx%)
Clinical examination:			
Heart murmur – no. (%)	xx (xx%)	xx (xx%)	xx (xx%)
Murmur radiation – no. (%)	xx (xx%)	xx (xx%)	xx (xx%)
Third heart sound – no. (%)	xx (xx%)	xx (xx%)	xx (xx%)
Positive HJR – no. (%)	xx (xx%)	xx (xx%)	xx (xx%)
Jugular ingurgitation – no. (%)	xx (xx%)	xx (xx%)	xx (xx%)
Edema – no. (%)	xx (xx%)	xx (xx%)	xx (xx%)
Ascites – no. (%)	xx (xx%)	xx (xx%)	xx (xx%)
Pulmonary attenuation – no. (%)	xx (xx%)	xx (xx%)	xx (xx%)
Pulmonary wheezing – no. (%)	xx (xx%)	xx (xx%)	xx (xx%)
Pulmonary Rales – no. (%)	xx (xx%)	xx (xx%)	xx (xx%)
Vital parameters:			
Diastolic blood pressure –mmHg (±SD)	xx±xx	xx±xx	xx±xx
Systolic blood pressure -mmHg (±SD)	xx±xx	xx±xx	xx±xx
Heart frequency – bpm (±SD)	xx±xx	xx±xx	xx±xx
Breathing frequency – rpm (±SD)	xx±xx	xx±xx	xx±xx
Oxygen saturation – % (±SD)	xx±xx	xx±xx	xx±xx
Temperature – °C (±SD)	xx±xx	xx±xx	xx±xx
Trigger of the current AHF episode			
Dietary and medication related causes			
Dietary indiscretion – no. (%)	xx (xx%)	xx (xx%)	xx (xx%)
Volume overload – no. (%)	xx (xx%)	xx (xx%)	xx (xx%)
Alcohol – no. (%)	xx (xx%)	xx (xx%)	xx (xx%)
Non-compliance to medication – no. (%)	xx (xx%)	xx (xx%)	xx (xx%)
Medication (NSAID, changes of diuretics) – no. (%)	xx (xx%)	xx (xx%)	xx (xx%)
Cardiac causes			
Myocardial ischemia / necrosis – no. (%)	xx (xx%)	xx (xx%)	xx (xx%)
Myocarditis – no. (%)	xx (xx%)	xx (xx%)	xx (xx%)
Uncontrolled hypertension – no. (%)	xx (xx%)	xx (xx%)	xx (xx%)
Arrhythmia (Afib, VT, bradycardia, AV-Block) – no. (%)	xx (xx%)	xx (xx%)	xx (xx%)
Progressive valvular disease (MI, AS) – no. (%)	xx (xx%)	xx (xx%)	xx (xx%)
Non-cardiac causes			
Pulmonary disease (PE, COPD) – no. (%)	xx (xx%)	xx (xx%)	xx (xx%)
Thyroid disorders – no. (%)	xx (xx%)	xx (xx%)	xx (xx%)
Physical, emotional, environmental stress – no. (%)	xx (xx%)	xx (xx%)	xx (xx%)
Infection – no. (%)	xx (xx%)	xx (xx%)	xx (xx%)
Anemia (<100g/l) – no. (%)	xx (xx%)	xx (xx%)	xx (xx%)
Unknown – no. (%)	xx (xx%)	xx (xx%)	xx (xx%)

Data are presented as absolute number and percentages (%) or means  $\pm$  standard deviations SD or median (25% to 75% interquartile range IQR) or median.

BMI= body mass index, CAD= coronary artery disease, PCI= percutaneous coronary intervention, ICD= implantable cardioverter-defibrillator, CRT= cardiac resynchronization therapy, COPD= chronic obstructive pulmonary disease, HJR= hepatjugular reflux, AHF= acute heart failure, NSAID= Nonsteroidal anti-inflammatory drugs, Afib= atrial fibrillation, VT= ventricular tachycardia, AV Block= atrial ventricular block, MI= mitral insufficiency, AS= aortic stenosis, PE= pulmonary embolism

Table 1 Baseline Clinical Characteristics and Medical History

## **8. Evaluation of treatment compliance and exposure**

### **y. Compliance to study drug and treatment**

The study drugs are administered to the patient during the index hospitalization by either the study physician and/or attending nurses following the study prescription forms. Nitrate capsules will be administered orally 3 times every 10 minutes whereas hydralazine will be given to the patient every 6 hours for 48 hours. Nitroderm patches will be adhered to the patient and the dosage adjusted according to the blood pressure.

#### **i. Compliance to study drug**

The study medication is administered only during the patient's hospitalization by either the study physician and/or attending nurses ensuring the best compliance possible.

**Table 2: Medication at baseline and during follow-up**

0

	Medication at baseline		Medication at 180 days FU			Medication at 360 days FU		
	Intervention arm (N=)	Standard of care arm (N=)	Intervention arm (N=)	Standard of care arm (N=)	p-value	Intervention arm (N=)	Standard of care arm (N=)	p-value
Beta blockers – no. (%)	xx (xx%)	xx (xx%)	xx (xx%)	xx (xx%)	x.xx	xx (xx%)	xx (xx%)	x.xx
ACE inhibitor – no. (%)	xx (xx%)	xx (xx%)	xx (xx%)	xx (xx%)	x.xx	xx (xx%)	xx (xx%)	x.xx
ARBs – no. (%)	xx (xx%)	xx (xx%)	xx (xx%)	xx (xx%)	x.xx	xx (xx%)	xx (xx%)	x.xx
Calcium antagonist – no. (%)	xx (xx%)	xx (xx%)	xx (xx%)	xx (xx%)	x.xx	xx (xx%)	xx (xx%)	x.xx
Diuretics– no. (%)	xx (xx%)	xx (xx%)	xx (xx%)	xx (xx%)	x.xx	xx (xx%)	xx (xx%)	x.xx
Aldosterone antagonist – no. (%)	xx (xx%)	xx (xx%)	xx (xx%)	xx (xx%)	x.xx	xx (xx%)	xx (xx%)	x.xx
Statins – no. (%)	xx (xx%)	xx (xx%)	xx (xx%)	xx (xx%)	x.xx	xx (xx%)	xx (xx%)	x.xx
Digoxin – no. (%)	xx (xx%)	xx (xx%)	xx (xx%)	xx (xx%)	x.xx	xx (xx%)	xx (xx%)	x.xx
Nitrates – no. (%)	xx (xx%)	xx (xx%)	xx (xx%)	xx (xx%)	x.xx	xx (xx%)	xx (xx%)	x.xx
Vitamin K antagonists – no. (%)	xx (xx%)	xx (xx%)	xx (xx%)	xx (xx%)	x.xx	xx (xx%)	xx (xx%)	x.xx
ASA – no. (%)	xx (xx%)	xx (xx%)	xx (xx%)	xx (xx%)	x.xx	xx (xx%)	xx (xx%)	x.xx
Clopidogrel – no. (%)	xx (xx%)	xx (xx%)	xx (xx%)	xx (xx%)	x.xx	xx (xx%)	xx (xx%)	x.xx

1

2

3 ACE inhibitor= angiotensin-converting-enzyme inhibitor, ARBs = Angiotensin II receptor blockers, ASA=acetylsalicylic acid.

4

5 Table 2 Medication

6

7 **z. Exposure to study drug**

8 **i. Extent of exposure**

9 Intervention arm: on top of the standard of care therapy, the patients will receive:

- 10 – sublingual nitrates three times every 10 minutes;
- 11 – hydralazine 25 mg p.o. four times a day (QID) for 2 days;
- 12 – nitroglycerin patches in a dosage between 40 to 80 mg in 24 h depending on systolic
- 13 blood pressure following the therapy schedule.
- 14 – If patients are pre-treated with either ACE-inhibitor or ARB, therapy with these agents
- 15 will be continued during the first 24 hours at the pre-existing dosage and afterwards
- 16 up-titrated following the therapy schedule starting with day 2.
- 17 Standard of care arm: patient will receive the standard of care treatment according to local
- 18 and current guidelines.

19 The study medication (hydralazine) will be provided by the pharmacy of the University

20 Hospital Basel.

21 **ii. Duration of exposure**

22 Six days after admission or until discharge from the index hospitalization.

23 **iii. Dose of exposure and concentration**

- 24 – sublingual nitrates: 0.8 mg glyceryl trinitrate, sublingual, 3 times every ten minutes.
- 25 Sublingual nitrates have an approximate onset of action of 1-3 minutes and a half-life
- 26 of 1–4 min.
- 27 – hydralazine 25 mg p.o. four times a day (QID) for 2 days. Half-life, 2–8 hours,
- 28 – nitroglycerin patches in a dosage between 40 to 80 mg in 24 h depending on systolic
- 29 blood pressure and for 5 days. Elimination half-life takes around 10 minutes.
- 30

31

32

33 **9. Evaluation of patients at follow-up**

34 Patient are contacted at 90, 180 and 360 days follow-up (telephone calls, letters). During the  
35 FU patients will be asked about current medication, functional NYHA class and additionally,  
36 to complete Quality of life (EQ-5D-3L) and Kansas City Cardiomyopathy Questionnaire  
37 (KCCQ).

38 **aa. Follow-up at 90 days**

39 The follow-up 90 days months contains a self-reported medicament list update, potential  
40 endpoints assessment, a functional NYHA class assessment and Quality of Life (EQ-5D-3L)  
41 assessment.

42 **bb. Follow-up at 180 days**

43 The follow-up 180 days months contains a self-reported medicament list update, potential  
44 endpoints assessment, a functional NYHA class assessment and Quality of Life (EQ-5D-3L)  
45 and KCCQ assessment.

46 **cc. Follow-up at 360 days**

47 The follow-up 360 days months contains a self-reported medicament list update, a functional  
48 NYHA class assessment and Quality of Life (EQ-5D-3L) and KCCQ assessment.

49 .

50

51 **10. Evaluation of efficacy parameters**

52 **dd. Analysis of primary, secondary, and other efficacy endpoints**

53 **i. Analysis of primary endpoint**

54 The primary endpoint will be analyzed using survival analysis for cumulative incidence (e.g.  
55 Cox regression, Kaplan-Meier and Hazard Ratio) and log rank testing for significance at 180  
56 days.

57 **ii. Analysis of secondary endpoints**

58 Secondary endpoints will be analyzed using the same approach as for the Primary endpoints  
59 and interaction test (p-value) will be conducted between the treatment group and the sub-  
60 group variables.

61 **iii. Analysis of other endpoints**

62 All other endpoints, including novel biomarkers or neurohormones not yet specified in the  
63 protocol will be analyzed using the same approach as for the **Secondary endpoints**.

64 **iv. Endpoint tables**

65 The following table will be produced and

66 Table 3 will be provided in the main publication:

67

68 **Table 3: Primary and secondary endpoint events**

Event	Intervention arm (N=)	Standard of care arm (N=)	Hazard Ratio (95%CI)	p-value
Primary composite endpoint – no. (%)†	xx (xx%)	xx (xx%)	x.xx (x.xx-x.xx)	x.xx
All-cause mortality — no. (%)	xx (xx%)	xx (xx%)	x.xx (x.xx-x.xx)	x.xx
Heart failure hospitalization – no. (%)	xx (xx%)	xx (xx%)	x.xx (x.xx-x.xx)	x.xx
Secondary endpoints – no. (%)	xx (xx%)	xx (xx%)	x.xx (x.xx-x.xx)	x.xx
All-cause mortality at 180 days.— no. (%)	xx (xx%)	xx (xx%)	x.xx (x.xx-x.xx)	x.xx
Heart failure hospitalization – no. (%)	xx (xx%)	xx (xx%)	x.xx (x.xx-x.xx)	x.xx
Death or re-hospitalization at 180 days. — no. (%)	xx (xx%)	xx (xx%)	x.xx (x.xx-x.xx)	x.xx
Need for ICU admission during initial hospitalization — no. (%)	xx (xx%)	xx (xx%)	x.xx (x.xx-x.xx)	x.xx
Acute coronary syndrome during initial hospitalization — no. (%)	xx (xx%)	xx (xx%)	x.xx (x.xx-x.xx)	x.xx
Symptomatic hypotension during initial hospitalization — no. (%)	xx (xx%)	xx (xx%)	x.xx (x.xx-x.xx)	x.xx
B-type natriuretic peptide (BNP) level – ng/l (±SD)	xx±xx	xx±xx	x.xx (x.xx-x.xx)	x.xx
at 48 hours	xx±xx	xx±xx	x.xx (x.xx-x.xx)	

69

	Intervention arm				Standard of care arm				Intervention vs standard of care	
	Baseline (N=)	Follow-up (N=)	Change FU vs Baseline	p-value	Baseline (N=)	Follow-up (N=)	Change FU vs Baseline	p-value	Mean difference of the change	p-value
at discharge										
Creatinine level – µmol/l (±SD)		XX±XX			XX±XX				x.xx (x.xx-x.xx)	
at 48 hours										
at discharge		XX±XX			XX±XX				x.xx (x.xx-x.xx)	
Changes in circumferences of both legs during initial hospitalization – cm (±SD)		XX±XX			XX±XX				x.xx (x.xx-x.xx)	
Blood pressure course over the first 6 days – mmHg (±SD)		XX±XX			XX±XX				x.xx (x.xx-x.xx)	
Time to disappearance of a third heart sound (if present initially) – days (±SD)		XX±XX			XX±XX				x.xx (x.xx-x.xx)	
Quality of life assessed at 90 days (±SD)	N= xx	N= xx	N= xx	x.xx	N= xx	N= xx	N= xx	x.xx	N= xxx	
Total triAS scale – mean score (±SD)	xx±xx	xx±xx	xx±xx	x.xx	xx±xx	xx±xx	xx±xx	x.xx	xx±xx	x.xx
Fractures due to fall within 180 days and 360 days – no. (%)		xx (xx%)			xx (xx%)				x.xx (x.xx-x.xx)	
Death or HF re-hospitalization at 360 days – no. (%)		xx (xx%)			xx (xx%)				x.xx (x.xx-x.xx)	

70

71

72

73

74

† The primary composite endpoint was the first occurrence of any component of the composite of death from all-cause mortality or hospitalization for heart failure in the time-to-event analysis. Data for all endpoint events, irrespective of whether the event was the patient's first occurrence of the event, are shown

Table 3 Endpoint assessment

75

76

77

78

It is expected that the Quality of Life (EQ-5D-3L) data will be reported in secondary publications:

79

